9.7.1.6.1 PRIMARY EFFICACY ANALYSIS

The primary analysis will be based on an intent to treat philosophy without regard to adherence to treatment. The primary analysis of the change from baseline in CDR-SB at 24 months will be performed to compare elenbecestat (E2609) 50 mg per day versus placebo using a linear mixed effects model for repeated measures (MMRM) on the FAS. The MMRM model will include baseline CDR-SB as a covariate, with treatment group, visit, randomization stratification variables (ie, region [7 levels], clinical dementia [yes, no], and concurrent AD medication use at randomization (Visit 2) [yes, no]), and treatment group-by-visit interaction as fixed effects. An unstructured covariance matrix will be employed to model the covariance of within subject effect; if MMRM fails to converge then a covariance structure with fewer parameters from the following list will be employed according to the prespecified order in the list until the MMRM converges. The list of covariance structure will include Heterogeneous Toeplitz, Toeplitz, Heterogeneous Compound Symmetry, and Compound Symmetry. This primary analysis will include all observed post baseline data of the change from baseline in CDR-SB without imputation of missing values. The treatment effect for elenbecestat (E2609) versus placebo will be compared at 24 months based on MMRM model. The LS means and difference in LS means between elenbecestat (E2609) treatment group and placebo, and corresponding 95% CI will be presented.

The null hypothesis is that there is no difference in the mean change from baseline in CDR-SB at 24 months between elenbecestat (E2609) 50 mg per day and placebo. The corresponding alternative hypothesis is that there is a difference in the mean change from baseline in CDR-SB at 24 months between elenbecestat (E2609) 50 mg per day and placebo.

The primary analysis will be repeated to minimize the impact of change in concomitant AD medications where efficacy data after initiation of new AD medications and increase of current AD medications will be censored.

The following sensitivity analysis will be conducted to evaluate the impact of missing data: the primary endpoint will be analyzed using ANCOVA after multiple imputation. The ANCOVA model will include baseline CDR-SB as a covariate, with treatment group and randomization stratification variables as factors.

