9.7.2 Determination of Sample Size

The sample size for this study is estimated based on comparison of elenbecestat (E2609) versus placebo with respect to the primary efficacy endpoint, the change from baseline CDR-SB at 24 months. Based on available ADNI data [amyloid positive, MMSE equal or greater than 24, late MCI (global CDR=0.5) populations from ADNI, ADNI 2 and ADNI GO] the mean and the standard deviation of the change from baseline in the CDR-SB at 24 months in the placebo group are assumed to be 1.75 and 2.05, respectively. Therefore, assuming a 25% reduction in the mean change from baseline CDR-SB at 24 months for the elenbecestat (E2609) 50 mg per day dose group compared to placebo with a common standard deviation of 2.05 and an estimated 30% dropout rate in this study, a total sample size of 1330 subjects, 665 subjects in each treatment group, will be required to detect the treatment difference between elenbecestat (E2609) 50 mg per day and placebo using a 2-sample t-test with 90% power at a significance level of 2-sided alpha =0.05.

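### If the MMRM fallback list is used beyond its first step, it reaches constant-variance structures that would probably understate the month-24 standard error of CDR-SB change; an unlikely event and a minor point

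*Protocol*

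**What the plan says.** Section 9.7.1.6.1 of the protocol starts from the most general model: "An unstructured covariance matrix will be employed to model the covariance of within subject effect". If that fit does not converge, a structure with fewer parameters "will be employed according to the prespecified order in the list until the MMRM converges". The order is: "The list of covariance structure will include Heterogeneous Toeplitz, Toeplitz, Heterogeneous Compound Symmetry, and Compound Symmetry". The synopsis has the same rule. Section 9.7.1.6.2 carries the primary MMRM over to the other continuous secondary endpoints.

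Section 9.7.2 gives the only information on spread: the mean and SD of change at month 24 in the "placebo group are assumed to be 1.75 and 2.05, respectively". No SD is given for any earlier visit. Section 9.1.2.1 schedules the CDR every three months, so there are eight on-treatment visits up to month 24. Section 9.7.1.6.2 also plans a random-coefficient slope analysis of the same change score.

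**The concern.** The response is change from baseline, which is zero at baseline by construction and is assumed to have SD 2.05 at month 24. If subjects decline at different rates, as the planned slope model supposes, the variance rises from visit to visit. Toeplitz and compound symmetry replace the visit-specific variances with a single value close to their average. The primary contrast is at month 24, where a rising variance is largest, so pooling makes the standard error too small and the p-value and confidence interval too favourable.

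The order makes this worse. The list gives up visit-specific variances at its second step and restores them at its third, so the better-suited structure is tried only if the less suitable one fails. A fallback is there to protect the 5% level when the main fit fails; this one may lose it.

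**Working it through.** **1. The plan's own figure.** Section 9.7.2 sizes the trial "assuming a 25% reduction in the mean change from baseline CDR-SB at 24 months", "with a common standard deviation of 2.05 and an estimated 30% dropout rate in this study", and "with 90% power at a significance level of 2-sided alpha =0.05".
- Difference: 0.25 × 1.75 = 0.4375.
- n per arm = 2 × (1.960 + 1.282)² × (2.05 / 0.4375)² ≈ 462.
- With 30% dropout: 462 / 0.70 = 660 per arm, 1320 in total.

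The plan states 1330, or "665 subjects in each treatment group". With 465 completers per arm the power is 90.2%. The sample size is reproduced and does not depend on the fallback list.

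**2. How far down the list.** Covariance parameters with eight visits:
- unstructured: 8 × 9 / 2 = 36
- heterogeneous Toeplitz: 8 + 7 = 15
- Toeplitz: 1 + 7 = 8
- heterogeneous compound symmetry: 8 + 1 = 9
- compound symmetry: 2

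Toeplitz is reached after two failures and compound symmetry after four.

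**3. Simple check, complete data.** The month-24 estimate is then the difference in means, and pooling gives

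SE ratio (model / true) = √(mean variance over visits / month-24 variance), type I error = 2 × [1 − Φ(1.96 × ratio)].

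This is exact for compound symmetry and approximate for Toeplitz.
- Variance proportional to time: √(13.5 / 24) = 0.75, type I error 0.142.
- Variance proportional to time squared: √(204 / 512) = 0.63, type I error 0.216.

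**4. Check with dropout.** Each structure was fitted by large-sample pseudo-likelihood to an assumed true covariance: eight visits, 665 per arm, 30% monotone dropout completely at random spread evenly over the visits, SD 2.05 at month 24. The model-based standard error was divided by the true one. Assumed truths:
- (a) constant SD, with correlation 0.8 per six months;
- (b) SD rising linearly from 1.50, same correlation;
- (c) random walk plus error, variance 0.145t + 0.72;
- (d) random slope plus error, variance 0.00605t² + 0.72.

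SE ratio and type I error for the homogeneous structures, type I error only for the heterogeneous ones:

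| Truth | SD, month 3 to 24 | Toeplitz | Compound symmetry | Het. Toeplitz | Het. CS |
|---|---|---|---|---|---|
| (a) | 2.05 to 2.05 | 1.00; 0.050 | 0.94; 0.065 | 0.050 | 0.051 |
| (b) | 1.50 to 2.05 | 0.86; 0.093 | 0.81; 0.110 | 0.050 | 0.051 |
| (c) | 1.07 to 2.05 | 0.78; 0.124 | 0.76; 0.139 | 0.076 | 0.059 |
| (d) | 0.88 to 2.05 | 0.72; 0.161 | 0.66; 0.195 | 0.095 | 0.064 |

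Unstructured gives 0.050 in every row. In (d), for example, Toeplitz reports 0.0877 against a true 0.1225, a ratio of 0.716.

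**5. Unconditional size.** If Toeplitz were reached with probability 5% (illustrative) in scenario (d): 0.95 × 0.050 + 0.05 × 0.161 = 0.056. At 1%: 0.99 × 0.050 + 0.01 × 0.161 = 0.051.

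**The case against.** The strongest reply is that the list will hardly be used. The planned analysis is unstructured, the first fallback already has visit-specific variances, and 36 covariance parameters are few for about 1330 subjects. This stands, and it sets the severity. For ADAS-cog14, MMSE and FAQ, measured every six months, it is stronger still: four visits need 4 × 5 / 2 = 10 parameters.

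Secondly, the protocol does not quantify growth in variance. This stands too. Under constant variance Toeplitz holds its level exactly. A reader might infer that change scores hardly differ between subjects at month 3; nothing in the document says so, and the calculation does not assume it.

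Thirdly, the choice of standard error estimator is commonly left to the SAP, which is not shown, so its absence here is not a fault in itself. That is right. The fault is the stated order, which an SAP could soften but which would still stand in the protocol.

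Finally, the planned sensitivity analysis, ANCOVA after multiple imputation, does not pool residual variance across visits, so an artificially small MMRM standard error would show beside it. That helps detection but does not replace the primary p-value.

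**Conclusion.** The point holds in conditional form. If the unstructured and heterogeneous Toeplitz fits both fail, and if the variance of change grows as assumed, the month-24 standard error is about 14 to 28% too small under Toeplitz and, if the list runs to its end, 19 to 34% too small under compound symmetry. The type I error is then about 0.09 to 0.16 and 0.11 to 0.20 respectively, against 0.051 to 0.064 for heterogeneous compound symmetry.

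A reader might infer that the trial's primary test runs at 9 to 20%. The document does not support that: those figures apply only after the convergence failures, and the overall level stays close to 0.05. The sizes rest on assumed SDs before month 24, dropout completely at random, and the eight on-treatment visits only.

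Allowing visit-specific variances is not a complete cure, since heterogeneous Toeplitz reaches 0.076 to 0.095 when correlations also change over time. Severity is minor.

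**What to change.** In section 9.7.1.6.1 and the synopsis, delete Toeplitz and Compound Symmetry, leaving Heterogeneous Toeplitz and then Heterogeneous Compound Symmetry. State that an empirical (sandwich) variance is used whenever a structure other than unstructured is fitted; this restores about 0.05 in large samples, including for heterogeneous Toeplitz. Align the SAP if it repeats the list. The cost is one sentence, with no change to data collection, conduct or sample size. Moving the homogeneous structures to the end would be a weaker remedy: it corrects the order but leaves them available.

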9.7.1.6.2 SECONDARY EFFICACY ANALYSES

The secondary analyses will be performed only if the primary analysis is significant. The treatment effect for elenbecestat (E2609) 50 mg/day versus placebo, for each secondary efficacy endpoint, will be tested using a sequential testing procedure at a significance level of 2-sided alpha = 0.05, ie, any test will start only if the test with higher hierarchical order is

significant. The final hierarchical order will be specified later in the statistical analysis plan before database lock.

Time to worsening of CDR scores by 24 months will be analyzed on the FAS using Cox regression model for treatment effect adjusting for randomization stratification factors. Time to worsening of a CDR score is defined as time from randomization to worsening of the CDR score (ie, the first worsening in 2 consecutive scheduled visits). For subjects whose CDR scores have not worsened by the end of study, the time to worsening of the CDR score will be censored at the date of last CDR assessment for these subjects.

Time to conversion to dementia for subjects who were not clinically staged as dementia at Baseline based on clinical diagnosis will be analyzed on the FAS using Cox regression model for treatment effect adjusting for randomization stratification factors. Proportion of subjects with dementia diagnosis at 24 months will be estimated using Kaplan—Meier method based on time to conversion to dementia based on clinical diagnosis. Time to conversion to dementia for subjects who were not clinically staged as dementia at Baseline based on clinical diagnosis is defined as time from randomization to conversion to dementia based on clinical diagnosis. For subjects without clinical dementia by the end of study, the time to conversion to dementia based on clinical diagnosis will be censored at the date of last dementia diagnosis.

The rate of change over time (mean slope) based on change from baseline in the CDR-SB will be analyzed using linear mixed effects (LME) models for multivariate normal data derived from a random coefficient model (slope analysis), where the mean slope in each group depends on a continuous assessment time. The LME model will include baseline CDR-SB, randomization stratification variables, assessment time, and treatment group-by-assessment time.

The other continuous secondary efficacy endpoints as defined above will be analyzed using the same MMRM model as the primary efficacy analysis to compare elenbecestat (E2609) 50 mg per day versus placebo on the FAS, using baseline value corresponding to the response variable in the model.

The relationship between clinical changes at 24 months (CDR-SB, ADAS-cog₁₄, MMSE, and FAQ) and changes in each of the biomarkers (amyloid PET, CSF t-tau and p-tau, vMRI, and fMRI) at 24 months, will be evaluated using an ANCOVA model. Changes in clinical scales at 24 months will be the response variables and either continuous or categorical change of biomarkers will be independent variables. The ANCOVA model will also include baseline value for clinical scale as a covariate, randomization stratification variables, treatment group as factors, and other terms as appropriate.

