baseline in CDR-SB without imputation of missing values. The treatment effect for elenbecestat (E2609) versus placebo will be compared at 24 months based on MMRM model. The LS means and difference in LS means between elenbecestat (E2609) treatment group and placebo, and corresponding 95% confidence interval (CI) will be presented.

The null hypothesis is that there is no difference in the mean change from baseline in CDR-SB at 24 months between elenbecestat (E2609) 50 mg per day and placebo. The corresponding alternative hypothesis is that there is a difference in the mean change from baseline in CDR-SB at 24 months between elenbecestat (E2609) 50 mg per day and placebo.

The primary analysis will be repeated to minimize the impact of change in concomitant AD medications where efficacy data after initiation of new AD medications and increase of current AD medications will be censored.

The following sensitivity analysis will be conducted to evaluate the impact of missing data: the primary endpoint will be analyzed using analysis of covariance model (ANCOVA) after multiple imputation. The ANCOVA model will include baseline CDR-SB as a covariate, with treatment group, and randomization stratification variables as factors.

Subgroup analysis (eg, *ApoE4* genotype) and additional sensitivity analysis for the primary endpoint will be performed as appropriate.

Analyses for Secondary Efficacy Endpoints

The secondary analyses will be performed only if the primary analysis is significant. The treatment effect for elenbecestat (E2609) 50 mg/day versus placebo, for each secondary efficacy endpoint, will be tested using a sequential testing procedure at a significance level of 2-sided $\alpha = 0.05$, ie., any test will start only if the test with higher hierarchical order is significant. The final hierarchical order will be specified later in the statistical analysis plan before database lock.

Time to worsening of CDR scores by 24 months will be analyzed on the FAS using Cox regression model for treatment effect adjusting for randomization stratification factors. Time to worsening of a CDR score is defined as time from randomization to worsening of the CDR score (ie, the first worsening in 2 consecutive scheduled visits). For subjects whose CDR scores have not worsened by the end of study, the time to worsening of the CDR score will be censored at the date of last CDR assessment for these subjects.

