Time to conversion to dementia for subjects who were not clinically staged as dementia at Baseline based on clinical diagnosis will be analyzed on the FAS using Cox regression model for treatment effect adjusting for randomization stratification factors. Proportion of subjects with dementia diagnosis at 24 months will be estimated using Kaplan–Meier method based on time to conversion to dementia based on clinical diagnosis. Time to conversion to dementia for subjects who were not clinically staged as having dementia at Baseline based on clinical diagnosis is defined as time from randomization to conversion to dementia based on clinical diagnosis. For subjects without clinical dementia by the end of study, the time to conversion to dementia based on clinical diagnosis will be censored at the date of last dementia diagnosis.

The rate of change over time (mean slope) based on change from baseline in the CDR-SB will be analyzed using linear mixed effects (LME) models for multivariate normal data derived from a random coefficient model (slope analysis), where the mean slope in each group depends on a continuous assessment time. The LME model will include baseline CDR-SB, randomization

stratification variables, assessment time, and treatment group-by-assessment time.

The other continuous secondary efficacy endpoints as defined above will be analyzed using the same MMRM model as the primary efficacy analysis to compare elenbecestat (E2609) 50 mg per day versus placebo on the FAS, using baseline value corresponding to the response variable in the model.

The relationship between clinical changes at 24 months (CDR-SB, ADAS-cog14, MMSE, and FAQ) and changes in each of the biomarkers (amyloid PET, CSF t-tau and p-tau, vMRI, and fMRI,) at 24 months will be evaluated using an ANCOVA model. Changes in clinical scales at 24 months will be the response variables and either continuous or categorical change of biomarkers will be independent variables. The ANCOVA model will also include baseline values for clinical scale as a covariate, randomization stratification variables, treatment group as factors, and other terms as appropriate.

Analyses for Biomarkers Endpoints

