9.1.2.1 Treatment Period

During Visit 2, the following assessments will be completed before the subject receives their first dose of study drug: MMSE, CDR, ADAS-cog₁₄, FAQ, and NPI-10. These assessments will provide baseline measurements for the study. Inclusion and exclusion criteria will again be reviewed together with concomitant medications and assessment of AEs. A single 12-lead ECG will be conducted. All ECG recordings will be evaluated by a central reader. The Columbia-Suicide Severity Rating Scale (C-SSRS) will also be administered. A baseline routine physical examination with dermatologic review, vital signs measurements, clinical laboratory testing (including viral characterization), urinalysis using urine dipstick, and a urine pregnancy test (females of child-bearing potential only), will be performed. Additional blood samples will be taken for immunologic assessments. Some of the immunologic assessment blood sample will be used to prepare isolated peripheral blood mononuclear cells (PBMCs) which will be stored for later testing. The results of some of the immunologic assessments will be provided to the DSMB for periodic review during the study. Whilst there is no prescribed order in which the assessments at each visit are to be performed, the subject component of the cognitive, functional and quality of life assessments are to be performed in the morning whenever possible, or consistently at the same time of the day and ideally should be completed before the more invasive procedures (eg, physical examination, ECG, blood draw).

Subjects will be randomized at Visit 2 (Day 1) to receive elenbecestat (E2609) 50 mg per day or placebo administered orally QD in the morning with or without food. Subjects will be encouraged to stay at the site for an appropriate period of time for observation following their first dose of study drug. Double-blinding to study drug will be in effect throughout the Treatment Period.

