9.3.1 Inclusion Criteria

Subjects must meet all of the following criteria to be included in this study:

1. MCI due to AD or Mild AD according to the National Institute of Aging – Alzheimer’s Association (NIA-AA) core clinical criteria and must have all of the following:
 - a. MMSE score equal to or greater than 24
 - b. CDR global score of 0.5
 - c. CDR Memory Box score of 0.5 or greater
2. A history of subjective memory decline with gradual onset and slow progression over the last 1 year before Screening; this MUST be corroborated by a study partner
3. Cognitive impairment of at least 1 SD from age-adjusted norms in total recall or delayed recall on the ISLT.
4. Positive biomarker for brain amyloid pathology as indicated by at least 1 of the following:
 - a. PET assessment of amyloid imaging agent uptake into brain. Note: amyloid PET screens will be performed according to local regulatory guidelines and thus may be restricted for those subjects who are not suitable for LP to obtain CSF for testing of eligibility.
 - b. CSF assessment of A β (1-42)

NOTE: Subjects may undergo both the amyloid PET and CSF assessments, but need a positive amyloid result in only 1 of the 2 procedures to confirm eligibility. Subjects who consent to amyloid PET or CSF for eligibility purposes are not required to participate in the amyloid PET or CSF longitudinal substudies. Use of a historical amyloid PET (conducted within 12 months before the planned date of randomization) is acceptable for determination of eligibility but will not suffice for the baseline assessment if the subject wishes to consent to the amyloid PET longitudinal substudy. The historical imaging data must be made available to the sponsor.
5. Male or female subjects between 50 and 85 years of age, inclusive at the time of consent
6. If receiving an AChEI or memantine or both for AD, must be on a stable dose for at least 12 weeks prior to Randomization. Treatment-naïve subjects with AD can be entered into the study.

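### Adding baseline CDR-SB to the two secondary Cox models is a free gain in efficiency; the planned tests are valid without it

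*Protocol*

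**What the plan says.** Section 9.7.1.6.2 sets the same covariates for both time-to-event secondary endpoints: each is to be "analyzed on the FAS using Cox regression model for treatment effect adjusting for randomization stratification factors". "Time to worsening of CDR scores by 24 months will be analyzed on the FAS using Cox regression model" is the synopsis wording for the first, and the adjustment named for each is the set of randomization stratification factors. Section 9.7.1.6.1 lists these as region (seven levels), clinical dementia (yes/no) and concurrent AD medication (yes/no).

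The second endpoint is restricted: "Time to conversion to dementia for subjects who were not clinically staged as dementia at Baseline based on clinical diagnosis will be analyzed" on the same terms.

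Elsewhere the plan does use the baseline score. The primary MMRM and its multiple-imputation ANCOVA include baseline CDR-SB (9.7.1.6.1). For the slope analysis, "The LME model will include baseline CDR-SB, randomization stratification variables, assessment time" and the treatment-by-time term. The other continuous secondary endpoints use the baseline of their own response variable.

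The CDR is done at Visit 2 before the first dose, and "These assessments will provide baseline measurements for the study" (9.1.2.1). FAS membership requires a baseline primary efficacy measurement (9.7.1.2), so no FAS subject lacks the covariate.

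**The concern.** The stratification factors say little about how close a subject is to an event. Inclusion requires a "CDR global score of 0.5" for everyone, so the global score has no spread at entry. Section 9.2.1 explains that the global score and CDR-SB are both derived from the same six domains, so differences in severity within global 0.5 lie in the boxes. That gives a reason, from the document itself, to expect baseline CDR-SB to predict worsening.

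For conversion, the analysis takes only subjects not staged as dementia. The clinical-dementia factor is then constant, and only region and AD medication remain.

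In a randomized comparison with a linear model, leaving out a prognostic covariate costs precision only. In a Cox model it also moves the estimated hazard ratio toward 1 relative to the ratio at a given covariate value, because high-risk subjects leave the risk set sooner. What is at stake is power on two secondary endpoints for which the protocol gives no power calculation.

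**Working it through.** **1. The plan's own figure.** It concerns the primary endpoint only. The difference is 0.25 × 1.75 = 0.4375 and the SD is 2.05. Then n per arm = 2 × (1.960 + 1.282)² × 2.05² / 0.4375² = 462 (463 with the exact t distribution). Allowing for 30% dropout, 463 / 0.70 = 661.4, so 662 per arm and 1324 in total, against 1330 stated. The figure reproduces. The protocol states no event rate, hazard ratio or power for either time-to-event endpoint.

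**2. Inputs.**
- From the protocol: 1330 subjects, about 1:1 allocation, 24 months, 30% dropout, two-sided 0.05, and a dementia stratum of at most about 25%. The conversion analysis therefore has about 0.75 × 1330 = 998, taken as 1000.
- Assumed: conditional hazard ratio 0.75; placebo 24-month event risk 30% or 50%; hazard ratio per SD of baseline CDR-SB of 1.3, 1.6 or 2.0; mean CDR-SB 1 SD higher in the dementia stratum. Region and AD medication were not simulated.

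**3. Method.** Event times are exponential with log-hazard = constant + ln(0.75) × arm + ln(HR per SD) × z, where z is standardized baseline CDR-SB. The constant is set to give the stated placebo risk, and dropout is exponential. Each trial is fitted as planned (arm plus clinical dementia for worsening, arm alone for conversion) and again with z added. There are 1000 trials per row. The Monte Carlo SE of a power near 60% is √(0.6 × 0.4 / 1000) = 1.5 points; both models are fitted to the same trials.

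**4. Results.**

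| Endpoint, placebo risk | HR per SD | Estimated HR, planned model | Power, planned | Power with CDR-SB | Gain (points) |
|---|---|---|---|---|---|
| Worsening, 30% | 1.3 | 0.751 | 69.5% | 71.6% | 2.1 |
| | 1.6 | 0.758 | 66.1% | 69.5% | 3.4 |
| | 2.0 | 0.764 | 63.6% | 69.7% | 6.1 |
| Worsening, 50% | 1.3 | 0.751 | 89.3% | 90.1% | 0.8 |
| | 1.6 | 0.760 | 88.5% | 90.8% | 2.3 |
| | 2.0 | 0.769 | 84.3% | 90.8% | 6.5 |
| Conversion, 30% | 1.3 | 0.751 | 57.3% | 58.1% | 0.8 |
| | 1.6 | 0.755 | 55.3% | 58.3% | 3.0 |
| | 2.0 | 0.757 | 54.8% | 60.3% | 5.5 |
| Conversion, 50% | 1.3 | 0.749 | 80.5% | 81.7% | 1.2 |
| | 1.6 | 0.761 | 77.5% | 80.9% | 3.4 |
| | 2.0 | 0.773 | 72.5% | 83.2% | 10.7 |

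With CDR-SB in the model, the estimated hazard ratio was 0.743 to 0.752 throughout.

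**5. Cross-check.** Schoenfeld's formula gives power = Φ(½ √events × |ln HR| − 1.96). At 300 events this is 70.2%, 66.2% and 61.9% for hazard ratios of 0.75, 0.76 and 0.77. A shift of 0.01 in the hazard ratio is worth about 4 points, which agrees with the table.

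**6. Stronger prognostic values.** A separate set of runs used log-hazard ratios of 0.5, 0.8 and 1.0 per SD, which are hazard ratios of e^0.5 = 1.65, e^0.8 = 2.23 and e^1.0 = 2.72.
- Conversion: power rises from 60% to 65%, 53% to 62% and 46% to 58%, gains of 5, 9 and 12 points.
- Worsening, against the model that keeps the dementia factor: 70% to 73%, 65% to 72% and 63% to 73%, gains of 3, 7 and 10 points.

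**7. Validity and downside.** With no treatment effect (1500 trials, 40% event risk), rejection rates were 4.7-4.8% for the planned model and 4.4% with CDR-SB. If baseline CDR-SB is not prognostic at all, adding it changes power by no more than 0.3 points.

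**The case against.** The case for leaving the models alone has substance.

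- **No error is shown.** The planned test is valid, and a hazard ratio adjusted for strata alone is a legitimate, more marginal measure. A reader might infer that the planned estimate is biased or the analysis wrong; the null simulations and the nature of the estimand do not support that. This stands.
- **There is no contradiction in the plan.** The models that carry a baseline score have a continuous response, and most use that response's own baseline. Conversion is a clinical diagnosis with no numeric baseline, and global CDR starts at 0.5 for everyone. Choosing CDR-SB is therefore a judgement. This stands, but section 9.2.1 supports the choice and nothing in the plan argues against it.
- **The SAP could add the term.** The protocol does not say these are the only covariates. True, but it names them outright, and the model as stated omits CDR-SB.
- **Larger losses can be produced.** For worsening with 35% placebo events and a log-hazard ratio of 1.0 per SD, a model with no covariate at all gave 58-60% power, against 73-74% with CDR-SB. The planned model keeps the dementia factor and gave 63-65%, so a loss of about 15 points is not supported. Nor is a drift to 0.80: with times grouped to three-month visits and Breslow ties, the CDR-SB-adjusted estimate was itself 0.757-0.764, so part of such a drift comes from tie handling.

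**Conclusion.** This is a free improvement, not a correction of an error. If baseline CDR-SB is moderately prognostic (hazard ratio 1.3-1.65 per SD), the planned models lose about 1-5 points of power. If it is strongly prognostic (2.0-2.7), they lose about 5-12. The planned hazard ratio moves from 0.75 to at most about 0.77 at 2.0 per SD. The point is strongest for conversion, where no factor in the model carries severity.

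All of this rests on assumed values for the treatment effect, the event risk and above all the prognostic strength, none of which the protocol gives. The upper range needs a strong predictor within a population already restricted to global CDR 0.5, and the document does not establish that.

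A reader might also infer that a miss on either endpoint would shut down the rest of the secondary testing. Section 9.7.1.6.2 leaves the hierarchical order to the SAP; if these endpoints come last, little or nothing lies below them. The primary test is unaffected either way.

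**What to change.** Before unblinding, change the covariate list of both Cox models in 9.7.1.6.2 and the synopsis (or state it in the SAP) to treatment, continuous baseline CDR-SB and the randomization stratification factors. For conversion, omit clinical dementia, which is constant there. Describe the hazard ratio in both cases as conditional on baseline severity.

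The cost is one phrase and one model parameter. No new data are needed and no FAS subject is lost. The only change in interpretation is that the reported ratio applies at a given baseline CDR-SB.
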